6.9 Blinding and Unblinding Methods

The blinding and unblinding methods will follow a double-blind study design although this is a single-blind study because the zileuton placebo is not completely matched to zileuton. The study products will not be identified by product names but by a unique randomization number. The randomization number is assigned to the subject upon completion of eligibility evaluation.

A list of non-sequential randomization numbers linked to each study arm will be created and forwarded to the DCP drug repository and the UACC research pharmacy. The DCP repository will ship the packaged aspirin, aspirin placebo, zileuton placebo, and bottles for repackaging zileuton to the UACC research pharmacy by randomization number. The UACC research pharmacy will order and repackage zileuton, as needed. The study products will be identified with the subject randomization number but with no product information on the label. Participant ID stickers will be supplied by the DCP drug repository to the UACC research pharmacy who will apply the clinical labels when a participant is randomized.

The UACC research pharmacy will dispense the product to the study staff for distribution to participants based on the assigned randomization number. Study staff will submit the returned bottles to the UACC research pharmacy for pill count. None of the staff interacting with participants will know the link between randomization number and actual product. This process will allow the study to remain blinded to all study personnel and participants. The code that identifies the product will be kept by the UAZ Consortium Biometry Director, the study statistician or the data manager.

Unblinding is not expected to occur until all participants complete the intervention and data entry is complete. Study agents may be unblinded by the Principal Investigator or, in her absence, a Co-Investigator after discussion with the NCI medical monitor, if possible, in the event of a serious adverse event if deemed medically necessary. If the NCI medical monitor is not available and unblinding is deemed necessary, it should be done and the medical monitor can be notified subsequently. The investigator will notify the UAZ Consortium Biometry Director, the study statistician or the data manager that the blind is to be broken.

The NCI, DCP Medical Monitor and/or Scientific Monitor must be notified that the blind has been broken.

DCP Medical Monitor:

6.10 Agent Destruction/Disposal

At the completion of investigation, the UACC research pharmacy will destroy and dispose of the study agent per standard operating procedures.

7. CLINICAL EVALUATIONS AND PROCEDURES
7.1 Schedule of Events

Procedure/ Evaluation	Pre Intervention		Intervention ²				Visit 6 Wk 14 Follow-Up
	Visit 1 Screening	Washout ¹	Visit 2 Baseline Specimen Collection/ Randomization /Intervention ⁷	Visit 3 Wk 4 Interim Study Visit	Visit 4 Wk 8 Interim Study Visit	Visit 5 Wk 12 End-of- Intervention	
Informed Consent	X						
Eligibility assessment	X						
Medical history	X						
CBC-diff, CMP ³ , PT/PTT ⁶	X					X	
Hepatic panel ⁸				X	X		X
Vitals (height, weight, temp, BP, heart rate)	X ⁴		X	X	X	X	
Physical Exam	X						
Karnofsky performance status	X						
Nasal brushing			X			X	X
Buccal sampling			X			X	X
Smoking history	X						
Current tobacco assessment	X		X	X	X	X	
Cessation of non-study ASA/NSAIDs		X	X	X	X	X	
Urine pregnancy test ⁵	X		X	X	X	X	
Blood for plasma salicylate/ASA/zileuton/AA oxylipins			X			X	X ¹⁰
Urine for PGE-M, LTE(4) & cotinine level ⁹			X			X	X ¹¹
Concomitant Medications	X		X	X	X	X	X
Dispense Study Agent			X	X	X		
Collect Study Agent				X	X	X	
Review Agent Diary/Record				X	X	X	
Adverse Events			X	X	X	X	X
Telephone/email Contact		X					

¹ Wash out period will be a minimum of 4 weeks if subject has taken ASA, NSAIDs or leukotriene antagonists within the preceding 2 weeks.

²Agent intervention to be 12 (± 1) weeks.

³CMP includes serum glucose, urea nitrogen, creatinine, sodium, potassium, chloride, bicarbonate, total protein, albumin, calcium, alkaline phosphatase, ALT, AST, total bilirubin. Calculations included with the CMP are: BUN/creatinine ratio, anion, gap, globulin, alb/glob ratio.

⁴Height required at Visit 1 only

⁵For women of childbearing potential

⁶Screening visit only.

⁷Randomization to occur within 30 days of consenting unless significant scheduling problems arise.

⁸Hepatic panel includes total protein, albumin, globulin, alb/glob ratio, alkaline phosphatase, ALT, AST, total bilirubin, direct bilirubin.

⁹Urine may be collected for a cotinine level at the screening visit to establish smoking status at the discretion of the Principal Investigator. If collected at the screening visit, it will serve as the baseline and will not be repeated at baseline visit.

¹⁰ AA oxylipins only.

¹¹PGE-M and LTE(4) only.

¹²Week 14 follow-up visit may be performed 10-14 days following end of intervention.

7.2 Prestudy Evaluation/Screening

Potential participants will undergo a brief interview to determine initial eligibility. During this interview, the study procedures and risks will be reviewed. Those who are interested in participating in the study and have been determined initially eligible will be scheduled for a clinic visit.

At the initial clinic visit (Visit 1, Screening Visit), the IRB-approved consent form will be reviewed with each potential study subject. All participants will be required to read and sign the consent form prior to enrollment. Once informed consent is obtained from provisionally eligible participants, they will be entered into the study and subjected to the following procedures:

A complete medical history of each subject including prior major illnesses, ongoing medical conditions, and ongoing medications will be obtained at baseline. Participants who are found to have any of the illnesses or use medications listed in the Exclusion Criteria (section 4.2) will be ineligible for the study.

All participants will undergo a brief physical exam at baseline to obtain height, weight, blood pressure, pulse, temperature measurements, a brief physical exam consisting of an examination of the heart, lungs and abdomen, and Karnofsky performance status assessment.

Blood samples will be collected for complete blood count (CBC) with differential, comprehensive metabolic panel (CMP), and PT/PTT. These blood tests are required to determine subject eligibility and for safety monitoring. Women of childbearing potential will have a urine pregnancy test. Concurrent medications, supplement use, and tobacco use will also be collected. Urine may be collected at the screening visit for cotinine level to establish smoking status, at the discretion of the Principal Investigator.

Once determined eligible, study participants who have taken ASA or NSAIDs within the preceding 2 weeks will undergo a washout period (minimum of 4 weeks) where no further ASA, NSAIDs or leukotriene antagonists will be allowed. Study participants will be provided with a daily diary for recording any adverse events and an intake calendar for recording medication usage.

7.3 Evaluation During Study Intervention

Study participants will return to the clinic for baseline specimen collection (Visit 2). During the visit, weight, blood pressure, pulse, temperature will be measured. A blood sample will be collected for plasma salicylate, ASA, zileuton levels and AA oxylipin analysis. Urine will be collected for PGE-M, LTE(4), and cotinine levels. If urine cotinine level was collected at the screening visit, it will serve as the baseline and will not be repeated at baseline visit. Participants will undergo a baseline nasal epithelium collection via cytology brushing of the nasal turbinate (see Section 7.6) for gene expression analysis. Buccal cells will also be collected (see Section 7.6) and archived as a reserved specimen for gene expression analysis and karyometric analysis. Women of childbearing potential will have urine pregnancy tests prior to receiving study agent at Visits 1 and 2 and also at Visits 3, 4, and 5.

Post baseline specimen collection, participants will be randomized to receive ASA 81 mg daily + Zileuton (Zyflo) 2 x 600 mg BID or placebos for 3 months. Participants will be supplied with a 6-week supply of study agents (to ensure sufficient agent supply until the interim visit), a study agents intake diary and AE diary.

Participants will return for two interim study visits (Visit 3, after 4±1 weeks of agent intervention and Visit 4, after 8±1 weeks of agent intervention). These visits will include vital signs, blood for hepatic panel, check of study agent intake, and a current tobacco use assessment. Concomitant medications and AEs will be

reviewed. Participants will return any unused study agents and receive the next 6-week supply of study agents.

7.4 Evaluation at Completion of Study Intervention

Participants will take study agents for 12 (\pm 1) weeks and return for the end-of-intervention visit (Visit 5). Participants will take the last dose of the study agents the morning of the end-of-intervention visit. When feasible, this visit will be scheduled between 4-6 hours after the last morning dose of ASA to allow for assessment of plasma ASA concentrations. At this visit, participants will return unused study agents. Evaluations will include vital signs, CBC and CMP panel, check of study agents intake, a current tobacco use assessment, and collection of nasal brushing (for gene expression), urine (for PGE-M, LTE(4), cotinine), blood (for plasma salicylate, ASA, zileuton and AA oxylipin analysis), and buccal cells (for banking and karyometric analysis). Concomitant medications and AEs will be assessed. The study agent diary will be collected.

7.5 Post-intervention Follow-up Period

Study participants will be instructed to continue to record adverse events and concomitant meds and return for a post-intervention follow-up visit (Visit 6) 10-14 days after the end of intervention visit. The AE and concomitant meds diaries will be collected, AEs will be assessed and study participants will have a hepatic panel done. A collection of nasal brushing (for gene expression), urine (for PGE-M, LTE(4)), blood (for plasma AA oxylipin analysis), and buccal cells (for banking and karyometric analysis) will be done.

7.6 Methods for Clinical Procedures

Nasal epithelium collection: A nasal speculum will be used to spread one of the nares while a standard cytology brush will be inserted underneath the inferior nasal turbinate. The brush will be rotated in place for 3 seconds, removed, and immediately placed in 1 ml of RNAProtect Cell solution. The same nare will be brushed again with another cytology brush as described above and immediately placed in RNAProtect Cell solution.

Buccal cell collection: The subject's mouth will be inspected for oral lesions so these areas can be avoided during the collection of the buccal cells. Participants will be instructed to rinse their mouths with tap water for 10 seconds before collection. First, a cytology brush will be used on one cheek using a twirling motion while moving the brush downward while applying counter pressure with their fingers against the external cheek; this will be done only once. Additionally, a cheek scraper will be rubbed in a firm fashion 5-10 times while applying counter pressure on the external cheek; this will be done 5 times using 5 individual scrapers on alternating cheeks as possible. The scrapers will be gently rinsed in RNAProtect Cell solution with the final scraper tip left in the RNAProtect Cell solution vial.

8. CRITERIA FOR EVALUATION AND ENDPOINT DEFINITION

8.1 Primary Endpoint

The primary endpoint is to compare changes in a smoking-related gene expression signature of nasal epithelium after ASA + Zileuton versus placebo.

8.2 Secondary Endpoints

The secondary endpoints are:

- To assess the impact of ASA and zileuton on three lung cancer gene signatures (an 80-gene bronchial signature, a PI3K pathway gene signature and a nasal diagnostic gene signature) and to compare this to placebo control.
- To determine whether the change in the smoking-related gene expression signature and the three lung cancer gene signatures of nasal epithelium persists 10-14 days off agent intervention.
- To measure urinary PGE-M and LTE(4) levels in current smokers after ASA and zileuton.
- To assess the safety in current smokers of 12 week exposure to ASA and zileuton.
- To evaluate a gender effect in the modulatory effects of ASA and zileuton on smoking-related gene expression signature.
- To explore the effect of ASA and zileuton on the metabolomics profile of the arachidonic acid pathway.
- To explore, in a discovery-driven fashion, the effect of ASA and zileuton on whole-genome gene expression.
- To analyze the impact of ASA and Zileuton on karyometric analysis of buccal cells.

8.3 Off-Agent Criteria

Participants may stop taking study agent for the following reasons: completed the protocol-prescribed intervention, adverse event or serious adverse event, inadequate agent supply, noncompliance, concomitant medications, or medical contraindication. Participants will continue to be followed, if possible, for safety reasons and in order to collect endpoint data according to the schedule of events.

8.4 Off-Study Criteria

Participants may go 'off-study' for the following reasons: the protocol intervention and any protocol-required follow-up period is completed, adverse event/serious adverse event, lost to follow-up, non-compliance, concomitant medication, medical contraindication, withdraw consent, death, determination of ineligibility (including screen failure), pregnancy.

8.5 Study Termination

NCI, DCP as the study sponsor has the right to discontinue the study at any time.

9. CORRELATIVE/SPECIAL STUDIES

9.1 Rationale for Methodology Selection

In this proposal we have chosen to measure nasal gene expression using Affymetrix Human Gene 1.0 ST microarrays. The microarray technology is ideal for this proposal because of its cost, ability to estimate gene expression for over ~19,000 genes, previously demonstrated successful use in measuring nasal gene expression.²² and ease of data analysis. The ability to measure additional genes not included in the smoking biomarker is advantageous because it will allow us to look at gene expression alterations associated with ASA and zileuton that are not part of the biomarker. Thus, we have chosen to use microarrays because they are cheaper than next-generation transcriptome sequencing, provide more information than qPCR, and allow us to assess the smoking biomarker in the proposed study using the same platform in which it was developed.

Urinary PGE-M and LTE(4) will be measured by sensitive and specific liquid chromatography-tandem mass spectrometry assays.^{43,29} These assays have been applied to measure urinary PGE-M and LTE(4) levels in smokers.

Urinary cotinine levels will be determined using a commercially available ELISA (GenWay Biotech). This assay kit is a competitive immunoassay designed for the measurement of cotinine in human urine samples.

Plasma concentration of salicylate and ASA will be analyzed by a published high performance liquid chromatography assay.⁴⁴ This assay has been applied to determine the concentration time course of ASA and salicylate following oral administration of 100-500 mg ASA.

A comprehensive panel of AA metabolites will be analyzed by a LC/MS/MS based method developed in [name] laboratory.³³ Currently, about 87 metabolites of arachidonate and linoleate metabolism emanating from COX, LOX, and CYP dependent metabolism can be routinely measured in serum, BALF and urine samples.^{30, 28,34,45}

9.2 Comparable Methods

The methods proposed to collect nasal epithelial cells and to measure nasal gene expression have been published previously.²² The methods proposed for microarray data analysis are widely published and used, and we expect the data generated in this study will be able to be compared to existing microarray data. Comparing data and establishing relationships between microarray datasets is very common and there are hundreds of manuscripts in Pubmed demonstrating this.

The methods for urinary PGE-M, LTE(4), cotinine and plasma salicylate and zileuton are standard methodologies used in other research studies. The method for AA oxylipins provides the most comprehensive profiling of the AA metabolites. The resulting data will be able to be compared to existing data.

10. SPECIMEN MANAGEMENT

10.1 Laboratories

Clinical chemistry and hematology panels will be outsourced to a contracted commercial diagnostic laboratory service (i.e., Sonora Quest). If urine is collected for a cotinine level at the screening visit, it will also be outsourced to Sonora Quest laboratory.

The urine and plasma biomarker analysis will be conducted in the laboratory of [name] which is located in the University of Arizona Cancer Center. All specimens will be labeled with the participant study number. [name] and laboratory staff will be blinded to the study intervention. Buccal cell collections will be stored in the laboratory of [name].

Nasal epithelium gene expression analysis will be conducted in the Division of Computational Biomedicine at Boston University and The Boston University Microarray Core overseen by [name]. All specimens will be labeled with the participant study number. [name] and laboratory staff will be blinded to the study intervention.

AA oxylipin analysis will be conducted in the laboratory of [name] located in the University of Arizona Cancer Center. The analysis will be overseen by [name]. All specimens will be labeled with the participant study number. [name] and laboratory staff will be blinded to the study intervention.

10.2 Collection and Handling Procedures

Blood for clinical chemistry, hematology and coagulation panels

Ten milliliters of blood (1 x 7 ml SST tube; 1 x 3 ml Lavender-EDTA tube) will be collected at screening and at the end of intervention for CBC with diff and CMP. A 2.4 milliliter Blue top tube will be collected at screening for PT and PTT. The SST tube will be held at room temperature for 30 min and then centrifuged. The lavender EDTA tube and blue top tube will be gently inverted to mix for anticoagulation. Blood tubes will be prepped, labeled, and packaged according to the recommendation from the diagnostic laboratory. All samples will be refrigerated prior to transfer to the commercial laboratory and sent for immediate analysis.

Urine for pregnancy test

A single void urine will be collected and tested for pregnancy in the clinic according to package instructions.

Urine for cotinine, PGE-M and LTE(4)

A single void urine will be collected and labeled with the participant study number, type of specimen and visit number. Urine will be aliquoted into 4 x 5 ml cryotubes and 4 x 2 ml cryovials and stored at (-80)°C until analysis.

Blood for salicylate, ASA and zileuton level

Ten milliliters of blood will be collected in heparinized vacutainer tubes for plasma salicylate/ASA and zileuton assay. Blood will be immediately chilled, and the plasma will be separated by centrifugation at 4°C within 15 min. The plasma will be aliquoted into 6 x 2 ml cryovials and stored at (-80)°C until analysis.

Blood for AA oxylipin analysis

Five milliliters of blood is collected into blue cap EDTA tubes and then plasma is separated into 300 uL aliquots. A stabilizing solution will be spiked into the plasma to provide 0.2% final concentration of triphenylphosphine (TPP) and butylated hydroxytoluene (BHT). The plasma aliquots will be stored at (-80)°C until analysis.

Nasal epithelium brushings

All nasal brushing samples will be preserved in RNAprotect Cell Reagent (Qiagen) upon collection and stored at (-80)°C. Specimens will be labeled with the participant study number, type of specimen and visit number. Specimens will be shipped on dry ice to [name] laboratory for analysis.

Buccal cell collection

Buccal cells from 5 cheek scraping collections will be preserved in RNAprotect Cell Reagent (Qiagen) upon collection and stored at (-80)°C. Buccal cells from one cytology brushing will be transferred to glass slides by firmly rolling the brush onto two collection slides. Cells will be allowed to adhere to slide for two minutes. Then place slides in 10 percent neutral buffered formalin for 10 minutes. Slides will then be stained using a standard eosin and hematoxylin method designed to enhance nuclear contrast.

10.3 Shipping Instructions

All shipments must be in compliance with International Air Transport Association (IATA) Dangerous Goods Regulations and institutional policies and procedures. Current shipper and institutional procedures must be followed. Biologic specimens (Category B, UN3373) will be in leak-proof primary and secondary receptacles with puncture resistant packaging and absorbent material. Shipments are to be preceded with phone contact to the receiving lab or alternate (see phone numbers below) to assure the shipment will be met and processed promptly.

Nasal brushing samples will be shipped to:

[name] Laboratory
Attn: [name]
Boston University School of Medicine
[name]
[name]
[name]
[contact]

Urine, plasma, and buccal cell collections will be placed on dry ice and hand delivered or shipped to [name] laboratory for final storage and analysis.

10.4 Tissue Banking

Biologic specimens collected during the conduct of each clinical trial that are not used during the course of the study will be considered deliverables under the contract and thus the property of the NCI. At study completion, NCI reserves the option to either retain or relinquish ownership of the unused biologic specimens. If NCI retains ownership of specimens, the Contractor shall collect, verify and transfer the requested biologic specimens from the site to a NCI-specified repository or laboratory at NCI's expense.

11. REPORTING ADVERSE EVENTS

DEFINITION: AE means any untoward medical occurrence associated with the use of a drug in humans, whether or not considered drug related. An AE can therefore be any unfavorable and unintended sign), symptom, or disease temporally associated with participation in a study, whether or not related to that participation. This includes all deaths that occur while a participant is on a study.

Please note that all abnormal clinical laboratory values that are determined to be of clinical significance based on a physician's assessment are to be reported as AEs. Those labs determined to be of no clinical significance or of unknown clinical significance (per the physician's assessment) should not be reported as AEs. Any lab value of unknown clinical significance should continue to be investigated/followed-up further for a final determination, if possible.

A list of AEs that have occurred or might occur (Reported Adverse Events and Potential Risks) can be found in §6.2, Pharmaceutical Information, as well as the Investigator Brochure or package insert.

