1.2 Secondary Objectives

- To assess the impact of ASA and zileuton on three lung cancer gene signatures (an 80-gene bronchial signature, a PI3K pathway gene signature and a nasal diagnostic gene signature) and to compare this to placebo control.
- To determine whether the change in the smoking-related gene expression signature and the three lung cancer gene signatures of nasal epithelium persists 10-14 days off agent intervention.
- To measure urinary prostaglandin E metabolite (PGE-M) and leukotriene E(4) (LTE(4)) levels in current smokers after ASA and zileuton.
- To assess the safety in current smokers of 12 week exposure to ASA and zileuton.
- To evaluate a gender effect in the modulatory effects of ASA and zileuton on smoking-related-gene expression signature.
- To explore the effect of ASA and zileuton on the metabolomics profile of the arachidonic acid pathway.
- To explore, in a discovery-driven fashion, the effect of ASA and zileuton on whole-genome gene expression.
- To analyze the impact of ASA and Zileuton on karyometric analysis of buccal cells.

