6.2.3 Combination of Aspirin and Zileuton

No combination studies of aspirin and zileuton have been reported. Co-administration of aspirin (294 mg/kg-diet) with A-79175 (75 mg/kg diet), a 5-LOX inhibitor structurally related to zileuton, did not produce any gross pathological changes in the liver, kidney, stomach, intestines, or lungs of mice following 25 weeks of treatment.¹¹

There are no published human safety data concerning the concomitant use of aspirin and zileuton in healthy individuals, although no pharmacokinetic or pharmacodynamic interactions were observed in a published study of 24 healthy volunteers co-administered the mixed COX-1/COX-2 inhibitor naproxen (500 mg) and zileuton (800 mg).⁴⁰ The drug combination had no effect on plasma concentration-time curves when compared with either agent given alone. Moreover, there was no evidence the drug combination altered serum LTB₄ or thromboxane B₂ levels beyond that observed with either naproxen or zileuton alone. Blockade of 5-LOX did not produce additive GI AEs typically associated with naproxen administration. This is in agreement with reports of reduced GI toxicity associated with dual COX/5-LOX inhibitors such as licofelone.^{41, 42} Given these data, the risk of GI toxicity resulting from the combined administration of aspirin and zileuton appears to be low. The possibility of additive hepatic toxicity from the combined use of aspirin and zileuton cannot be completely ruled out since both drugs are metabolized by the liver.

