Descriptive statistics of the type and frequency of all adverse events will be generated, including 95% confidence intervals. For each type of the adverse events, a Fisher's exact test will be performed to compare the frequency of the adverse event between the two groups.

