13.7 Evaluation of Toxicity

All participants will be evaluable for toxicity from the time of their first dose of study agent.

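### Liver tests are drawn at five visits, but the only planned safety comparison counts adverse events that pass a physician's judgement; a descriptive by-arm summary of the measured values should be added

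*Combined protocol and SAP*

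**What the plan says.** Section 1.2 lists as a secondary objective: "To assess the safety in current smokers of 12 week exposure to ASA and zileuton". Section 6.2.3 reports no combination studies of the two drugs and adds: "The possibility of additive hepatic toxicity from the combined use of aspirin and zileuton cannot be completely ruled out". Section 6.2.2 cites a 12-week study of extended-release zileuton in which ALT reached three times the normal limits in 5 of 199 treated and 1 of 198 placebo patients. Two of the five treated cases were detected 14 days after treatment ended.

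Sections 7.1 to 7.5 schedule liver tests five times: within the metabolic panel at screening and week 12, and as a hepatic panel at weeks 4, 8 and 14.

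Section 11 sets the reporting rule: "all abnormal clinical laboratory values that are determined to be of clinical significance based on a physician's assessment are to be reported as AEs". Values in the group "Those labs determined to be of no clinical significance or of unknown clinical significance" are not to be reported as adverse events, although those of unknown significance are to be followed towards a final determination where possible.

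The safety analysis in section 13.5 has two parts: "Descriptive statistics of the type and frequency of all adverse events will be generated, including 95% confidence intervals", and "For each type of the adverse events, a Fisher's exact test will be performed" to compare the arms. Section 13.7 adds only who is evaluable: "All participants will be evaluable for toxicity from the time of their first dose of study agent". Section 13.9 mentions monitoring of adverse events and plans no formal interim analysis.

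**The concern.** The reporting rule is reasonable by itself. The gap appears when it is read with section 13.5. Because adverse events are the only safety data the plan analyses, the rule also decides which liver results are compared between arms. Five rounds of ALT, AST, alkaline phosphatase and bilirubin are collected, and no section of the plan provides a summary, threshold count or between-arm estimate for them.

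Two things are at stake. First, the prior evidence in section 6.2.2 is expressed as a rate of ALT above a fixed multiple of normal. An analysis of physician-selected events need not produce that rate, so the trial's hepatic results could not be set beside the evidence that motivated the testing. Second, what enters the comparison depends on a judgement. Section 6.9 calls the study single-blind because the zileuton placebo is not fully matched, although it also says that study personnel remain blinded. A summary of all measured values does not depend on that judgement.

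**Working it through.** **Route of a liver result into the analysis**

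| Liver result | Adverse event under section 11? | Compared by arm under section 13.5? |
|---|---|---|
| Abnormal, judged clinically significant | Yes | Yes, as an event count |
| Abnormal, significance unknown | No, unless later judged significant | No, unless later judged significant |
| Abnormal, judged not significant | No | No |
| Measured value, change from screening, or maximum | Not applicable | No analysis named |

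**What a count of the three-times category can show**

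Inputs: 33 randomised per arm (section 13.3); ALT rates from section 6.2.2.

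1. Cited rates: 5/199 = 2.5%; 1/198 = 0.5%. Both reproduce.
2. Expected events if those rates applied here: 33 × 0.025 = 0.83 active; 33 × 0.005 = 0.17 placebo.
3. Chance of no event in the active arm: 0.975^33 = 0.43.
4. Two-sided Fisher test: 5/33 versus 0/33 gives p = 0.053; 6/33 versus 0/33 gives p = 0.024. With no placebo events, six active events are needed.
5. Exact Fisher power, summing the binomial probabilities of all significant tables at 2.5% versus 0.5%: 0.013%.
6. Exact 95% upper limit when 0 of 33 are seen: 1 − 0.025^(1/33) = 10.6%.

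Step 5 assumes that every such elevation is counted. It therefore measures how rare the event is in a trial of 66, not what is lost through the clinical-significance rule. The documents do not allow that loss to be estimated.

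**Whether a comparison of means would do better**

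Assume the cited excess is a small subset, 2.5% versus 0.5%, with each affected participant shifted by k SD on the scale of change in log ALT. The mean difference is then (0.025 − 0.005) × k = 0.02k SD. Simulating a two-sided 5% t test at 33 per arm with k = 3, 5 and 8 gives power of about 5 to 6%, which is essentially the significance level. The documents give no SD for ALT, so k is an assumption, but the result is the same across that range.

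**The case against.** Several counter-arguments are sound, and they limit what can be claimed.

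- *Section 11 is a reporting rule and does not bar laboratory values from analysis.* Correct. Section 13 is silent on them; the gap comes from reading the two together.
- *Clinically significant liver abnormalities are compared.* Correct. A reader might infer that no liver finding ever reaches a between-arm test, but an abnormality judged significant becomes an adverse event and enters the Fisher test. A value of unknown significance can also become one after follow-up.
- *The low Fisher power does not measure harm from the rule.* Correct, as shown above. A test on the three-times category would have the same power.
- *Continuous ALT would reveal the hepatic signal.* This is the most tempting stronger reading, since a t test with 33 per arm has 80% power at a 0.70 SD mean difference. The documents do not support it: an excess confined to 2 participants in 100 would need k = 0.70/0.02 = 35 SD per affected participant to produce that difference. Only a general shift in ALT could be found that way, and no section predicts one.
- *The physician's judgement is biased.* Not shown. Section 6.9 says that staff interacting with participants will not know which product was assigned, and section 10.1 sends chemistry panels to an outside laboratory. Imperfect matching makes influence possible and no more.
- *Liver toxicity is not declared the leading risk.* Correct. Gastrointestinal effects are also named in section 6.2. The protocol says only that additive hepatic toxicity cannot be excluded.

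Review by the safety monitoring board every six months (section 12.4) is oversight and does not supply a prespecified between-arm summary. What remains is the missing summary.

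**Conclusion.** The point holds as a request for a prespecified descriptive analysis. Liver results enter the planned comparison only as adverse events that a physician has judged clinically significant. Other abnormalities, and all the measured values, are neither summarised nor compared by arm. The plan therefore need not produce a rate comparable to the 2.5% versus 0.5% in section 6.2.2.

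The size is modest. The primary endpoint is unaffected, and adding the summary does not give the trial useful power for a rare excess: about 0.8 versus 0.2 events are expected if the cited asthma-trial rates carry over and all 33 per arm contribute liver tests. Section 13.3 expects at least 20 per arm with evaluable endpoint data. If liver-test attrition were similar (an assumption), the expected counts fall to 20 × 0.025 = 0.5 and 20 × 0.005 = 0.1. The gain is completeness, comparability with the cited evidence, and less dependence on individual judgement.

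**What to change.** Add a paragraph to section 13.5 specifying, for ALT, AST, alkaline phosphatase and total bilirubin, and using every measured value whatever the clinical-significance judgement:

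- by-arm summaries at screening and weeks 4, 8, 12 and 14, with change from screening (for example on the log scale) and a between-arm difference with 95% CI;
- each participant's maximum post-baseline value as a multiple of the upper limit, by arm, with counts and exact 95% CIs for the ALT three-times category used in section 6.2.2;
- the number of participants contributing at each visit.

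Label the analysis descriptive. State that with 33 or fewer per arm it cannot reliably detect an excess of the size cited in section 6.2.2, so absence of a difference is not evidence of hepatic safety. Leave the adverse-event reporting rule in section 11 and the Fisher tests as they are.

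The cost is one or two tables from data already collected, with no new samples or visits. The downside is a set of unadjusted intervals, four analytes × four visits = 16 for change alone, to be read with the caution that section 13.5 already promises for secondary analyses.
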